11.2. CLINICAL AND IMAGE FOLLOW-UP

This will be done before discharge, in consultation at three, six, and 12 months and annually thereafter. All the visits have a window period to be carried out with additional tests within this protocol, one week before and one week after the due date.

First visit (Basal Visit).

- Assessment of patient history.
- Detailed physical assessment of the patient.
- Electrocardiogram.
- Analysis.
- Echocardiographic basal study, with ventricular *strain* measurements.
- Perform 6-minute test.

Follow-up visit at 3 months (more/less one week)

- Clinical assessment.
- Analysis.
- Events assessment.

Follow-up visit at 6 months (more/less one week)

- Clinical assessment.
- Analysis.
- Perform 6-minute test.
- Events assessment.

Follow-up visit at 12 months (more/less one week)

- Clinical assessment.
- Electrocardiogram.

Prognostic impact of cardiac amyloidosis in patients with severe aortic stenosis who underwent percutaneous implantation of an aortic prosthesis

- Analysis.
- Echocardiographic study with ventricular *strain* measurements.
- Events assessment.

Follow-up visit at 24 months (more/less one week)

- Clinical assessment.
- Analysis.
- Echocardiographic study.
- Events assessment.

11.3 WITHDRAWAL FROM THE STUDY

- A) Withdrawal of a patient from the study because they withdraw the consent.
- B) Withdrawal of the study due to transfer to another health area

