8. OBJECTIVES

8.1 PRIMARY OBJECTIVE

A multicentre prospective study of cohorts consisting of two cohorts from patients who have been implanted with percutaneous aortic prosthesis as treatment for the severe degenerative aortic stenosis and compare the overall mortality and that for

cardiovascular and admissions for heart failure in the 2-year follow-up of patients diagnosed with amyloidosis (by GT99 and EFP) versus those that do not have it.

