9. DESIGN

A multicentre, analytical, observational study of two cohorts. One cohort will be constituted by the patients to whom a TAVI will be implanted, and that meet non-invasive diagnostic criteria of TTR amyloidosis (capturing of radiotracer in grades 2 and 3 and absence of monoclonal gammopathy the PE of urine or serum). The other cohort will be constituted by patients whose TAVI implants do not meet the diagnostic criteria for TTR amyloidosis.

A clinical and echocardiographic follow-up will be done in all patients for two years.

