10. STATISTICAL ANALYSIS PLAN AND SAMPLE SIZE

10.1 STATISTICAL ANALYSIS

A descriptive analysis of both cohorts defining their clinical and angiographic profiles and a comparative study of the two groups (cohorts) will be performed. The categorical variables are expressed in percentages and the continuous as medium value \pm standard deviation. The relative risk and the “Hazard Ratio” will be used as measures of effect when variables are analyzed with a temporal component, always with a confidence interval of 95%. For the comparison of categorical variables, the Chi-square or the Fisher test will be used. To compare continuous variables, the “t” of student test or analysis of variance will be used. The variables of time to event, such as the analysis of event-free survival will be analyzed by using the Kaplan- Meier technique and will be supplemented by the log-rank test. The multivariate analysis of the adverse events predictors during the follow-up will be done by means of the Cox regression model, determining the Odds Ratio for each variable.

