10.1 SAMPLE SIZE

Based on the information available, around 15% of the patients to whom a TAVI has been implanted show signs of amyloidosis. Mortality at two years after a TAVI is about 17% and in patients with amyloidosis, it is estimated to be 40%. Based on this data, for a significance level of 5% (error $\alpha = 0,05$) and a power of 80% (error $\beta = 0,20$), a sample size of 306 patients is estimated, assuming 5% of follow-up losses, it was decided to include 321 patients. The results in which the calculations are based are given at 2 years, if not significant; monitoring would continue up to 3 years.

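### Section 11.3 withdraws patients who move to another health area, and no route is given to learn their deaths or admissions afterwards

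*Combined protocol and SAP*

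**What the plan says.** Section 11.3 has two entries. The first is "Withdrawal of a patient from the study because they withdraw the consent". The second is "Withdrawal of the study due to transfer to another health area". It does not say what happens to data already collected, whether outcomes are sought later, or how these patients enter the analysis.

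The primary objective (Section 8.1) compares all-cause mortality, and mortality that is "cardiovascular and admissions for heart failure in the 2-year follow-up of patients diagnosed with amyloidosis", with the same outcomes in patients without amyloidosis. Section 9 states: "A clinical and echocardiographic follow-up will be done in all patients for two years".

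On the schedule, Section 11.2 says: "This will be done before discharge, in consultation at three, six, and 12 months and annually thereafter". In the Section 12 work plan, event assessment takes place at the 3-month, 6-month, 1-year and 2-year visits, and Section 13.1 has the data logbook completed at each visit. If the two-year result is not significant, "monitoring would continue up to 3 years" (Section 10.1, Sample size).

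Time-to-event outcomes "will be analyzed by using the Kaplan- Meier technique and will be supplemented by the log-rank test", with Cox regression for the multivariable analysis (Section 10.1, Statistical analysis). No censoring rule and no sensitivity analysis for losses is given. The sample size allows for 5% losses to follow-up.

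**The concern.** Moving house is not a refusal to take part. Death, and usually hospital admission, can be learned without a site visit, so this loss is avoidable. As written, though, events are recorded only at consultations, and a transferred patient has no more of them.

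Two things are at stake. The first is information: the amyloidosis cohort is small, and each unobserved death there is a visible share of the total. The second is bias. Kaplan-Meier, log-rank and Cox methods all assume that censoring is unrelated to prognosis. Elderly patients may move nearer to family or into care because they are declining, in which case the patients censored are those at higher risk. The 5% allowance replaces numbers; it does not correct for such selection. A possible third year gives more time for transfers.

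**Working it through.** **Inputs from Section 10.1 (Sample size).** Amyloidosis prevalence 15%; two-year mortality 40% with amyloidosis and 17% as reference; alpha 0.05 (taken as two-sided); power 80%; 306 patients before losses, 5% losses, 321 enrolled.

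**The plan's own figures.** The hazard ratio implied by the two risks is ln(0.60)/ln(0.83) = 2.74. Schoenfeld's formula with a 15:85 split gives (1.960 + 0.842)² / [0.15 × 0.85 × (ln 2.74)²] ≈ 61 events. The pooled risk is 0.15 × 0.40 + 0.85 × 0.17 = 0.2045, and 61/0.2045 ≈ 299, within 3% of 306. Then 306 × 1.05 = 321.3, so 321. The sample size is not at issue here.

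**Expected counts.** Amyloidosis patients: 321 × 0.15 ≈ 48. Deaths among them: 48 × 0.40 ≈ 19. Losses at 5%: 321 × 0.05 ≈ 16. On the Schoenfeld approximation, power is 83.1% with all 321 patients ascertained and 81.2% with 5% non-informative loss.

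**Model for informative loss.** The documents give neither a transfer rate nor mortality after transfer, so what follows is assumed. Survival is exponential. A fraction m of a cohort is due to move at a time uniform over the two years. The hazard is multiplied by k = 3 or 5 after the move. With H = −ln(1 − p) the two-year cumulative hazard without a move, a mover's two-year survival is

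S(k) = (e^(−H) − e^(−kH)) / [(k − 1)H].

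- Amyloidosis, H = 0.5108: S(3) = (0.600 − 0.216)/1.0217 = 0.376, so mover mortality is 62.4%. S(5) = (0.600 − 0.078)/2.0433 = 0.256, so 74.4%.
- No amyloidosis, H = 0.1863: S(3) = (0.830 − 0.572)/0.3727 = 0.693, so 30.7%. S(5) = (0.830 − 0.394)/0.7453 = 0.585, so 41.5%.

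True cohort mortality is (1 − m)p + m(1 − S(k)). Kaplan-Meier with censoring at transfer sees only the pre-move hazard and stays at 40%. For unseen deaths, the chance that a mover is alive at the time of the move is (1 − e^(−H))/H = 0.40/0.5108 = 0.783. Unseen amyloidosis deaths are then 48 × m × (0.783 − S(k)).

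| Amyloidosis patients moving | Kaplan-Meier | True, k = 3 | True, k = 5 | Unseen deaths, k = 3 to 5 |
|---|---|---|---|---|
| 5% | 40% | 41.1% | 41.7% | 1.0 to 1.3 |
| 10% | 40% | 42.2% | 43.4% | 2.0 to 2.5 |
| 15% | 40% | 43.4% | 45.2% | 2.9 to 3.8 |

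**Effect on the comparison at 5% movers.** The hazard ratio is taken as ln(1 − p₁)/ln(1 − p₀), with p₁ the amyloidosis risk and p₀ the reference risk. Under censoring it is 2.74. With complete follow-up:

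- Both cohorts move equally, k = 3: risks 41.1% and 17.7%, hazard ratio 2.72. k = 5: 41.7% and 18.2%, hazard ratio 2.68.
- Only amyloidosis patients move, k = 3: 41.1% and 17%, hazard ratio 2.84. k = 5: 41.7% and 17%, hazard ratio 2.90.

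Censoring at transfer thus slightly overstates the contrast in the first case and understates it in the second.

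**The case against.** The best defence is that Section 11.3 is only two short entries. It nowhere says that vital status is discarded or that earlier data are dropped, and Section 9 points the other way by promising follow-up for everyone. That stands as far as it goes: a reader might infer deliberate discarding, and the text does not support that. But it does state a rule that transfer ends participation, and no section describes another way to collect events. The consent text was not available to this review, so it may already permit telephone or record follow-up.

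It is also tempting to say that losses will fall more heavily on the amyloidosis cohort. No section gives a transfer rate, a reason for moving, or a difference between cohorts, so this is an assumption. The 10% and 15% scenarios exceed the plan's own 5% allowance for all losses. At 5% the absolute bias is 1 to 2 points, against a sampling standard error of √(0.40 × 0.60/48) ≈ 7 points. This objection stands in full and limits the size of the point.

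Finally, a reader might infer that the study's power is in jeopardy. Losing 10% of the amyloidosis cohort at twice its mortality, with 5% non-informative loss in the other cohort, gives a hazard ratio of about 2.36 and power of about 64%. But that calculation drops the lost patients as missing, whereas the planned Kaplan-Meier and Cox analyses would keep their follow-up up to censoring. It does not describe this plan.

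**Conclusion.** The point holds as an avoidable gap and an internal conflict, not as a flaw that undermines the study. Section 11.3 ends follow-up for patients who still consent, against Section 9, and nothing visible supplies their deaths or admissions afterwards. Under the assumed model, the amyloidosis mortality estimate is low by about 1 to 2 points with 5% moving and by about 2 to 3.5 points with 10%. At 5%, the hazard ratio shifts by no more than about 0.16 (2.90 − 2.74), in a direction that depends on who moves. All of this rests on exponential survival, uniform transfer times and a three- to fivefold hazard after the move, none of which the documents supply. The documents do not establish that loss is informative or unequal between cohorts. The case for change is that the repair is cheap and protects the primary outcome.

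**What to change.** In Section 11.3, limit withdrawal to withdrawn consent and treat transfer to another health area as the end of site visits only. State that vital status and hospital admissions, with cause of death where possible, are sought to 24 months (36 if follow-up is extended) by telephone or health records, after checking that the consent covers this. In Section 10.1, state that patients are censored at last contact only if that search fails, and that losses are reported by cohort with reasons. Align Section 9 with the revised wording.

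The cost is an edit to the protocol, possibly a line in the consent, and telephone or record work for up to about 16 patients at the planned 5% loss.

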12. WORK PLAN

	Basal	3 months	6 months	1 year	2 years
Clinical history	X				
Informed Consent	X				
Clinical assessment	X	X	X	X	X
ECG	X		X	X	X
Analysis ¹	X		X	X	X
Protein electrophoresis	X				
Scintigraphy with tecnecio ⁹⁹	X				
Echocardiogram with strain	X		X	X	X
The 6-minute test	X		X		
Events assessment		X	X	X	X

1: includes: hemoglobin, hematocrit, lipid profile, NT-proBNP, TnT, electrolytes, C-reactive protein, creatinine, and glomerular filtrate.

13. DATA MANAGEMENT

13.1. DATA COLLECTION:

All the patients will receive standard treatment according to clinical practice guidelines and consensus in force. The criteria for inclusion/ exclusion will be assessed in all of them to confirm the feasibility of entering the study, which will be offered, explained, and then the appropriate informed consent collected. Subsequently, following the predefined protocol, a number of epidemiological variables, clinical, laboratory, electrocardiographic, echocardiographic, functionals, scintigraphy with Tc⁹⁹basals of the patient will be collected before discharge. All previously detailed. All the data will be collected in the Data Collection Logbook (DCL), which is designed to register all the data required in the protocol and collected by the researcher. The data on the DCL will be coded. The data entry will be done by the researcher or the person assigned by them, and then that data will be transferred to the database of the study. The researcher or the appointed person in their team commits to completing the DCL on each visit made by the participant. All data corrections in the DCL will be made by the researcher or the person assigned in their team in accordance with the instructions given. After the last visit from the participant and the closure of the DCL, the researcher must attest, by signing the DCL, the authenticity of the data collected in the DCL, the coherence between the data in the DCL and the data contained in the source document.

13.2 DATA CONFIDENTIALITY:

All documents and information provided to the researchers by the promoter regarding the study are confidential. Both the researcher and their collaborators undertake to use the information provided only within the framework of this study to carry out this protocol. This commitment remains as long as the confidential information has not been made public by the promoter. The protocol delivered to the researcher can be used by them or their collaborators to obtain informed consent from the participants entering the study. It should not be disclosed to third parties without the written consent of the promoter. This information will be treated in accordance with the rules of professional secrecy. The screening list must be completed when the researcher verifies that the participant can enter the study after confirming their record and medical history.

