vessels during the procedure but also those occurred in the monitoring where there is still no solid evidence regarding antithrombotic handling. 2, Atrioventricular conduction disorders requiring permanent pacemaker implantation in 20-40% of the patients. 3, Vascular complications of the accesses. 4, Residual valve by the malpositioning of the prosthesis (creating a high residual gradient or insufficiency). 5, Valvular degeneration and durability of the prosthesis.

Cardiac amyloidosis by transthyretin.

The amyloid myocardial infiltration by transthyretin monomers and oligomers (TTR) with misfolding(7) is a serious and under-diagnosed disease which predominantly affects men over 60 years old and presents itself with symptoms of heart failure, orthostatic hypotension, and syncope (8). The infiltration of the cardiac conduction system can generate branch blocks, atrioventricular blocks, and atrial fibrillation.

There are two types of amyloid that can infiltrate the myocardium: the amyloid light chain (AL or primary) within a monoclonal gammopathy, and the TTR amyloid. The latter in turn has two types of disease, familial, due to a mutation that causes transthyretin misfolding; and sporadic (formerly known as senile), which is due to incorrect folding of the common transthyretin. (8)

The prevalence of the TTR amyloidosis in patients with AoS to whom a TAVI is performed is estimated at 14-16%(9)(10) and 6% in those over 65 years old to whom a surgical valve replacement is performed(11). It is especially associated with the AoS phenotype of low-flow and low gradient (9). Cardiac amyloid deposits were found in nearly one-third of autopsies of patients with TAVI implants who died before 30 months(12), and the patients with AoS and amyloidosis have a prognosis similar to those with amyloidosis without AoS (13). It all states that the amyloidosis implies a worse prognosis (11). It is also suggested that amyloid infiltration may increase the requirements of permanent pacing (14).

Recently the benefits of treatment with Tafamidis on patients with cardiac amyloidosis by TTR have been published. (15)

Non-invasive diagnosis of cardiac amyloidosis.

The echocardiogram is used to find interesting data of amyloidosis: increased thicknesses of the atrioventricular valves, interatrial septum valves or the free wall of

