11. PATIENTS FOLLOW-UPS

11.1 INITIAL PATIENT ASSESSMENT

An initial inclusion visit will assess whether the patient is a candidate who meets the inclusion criteria and none of the exclusion ones. After being informed, if they accept, the informed consent must be signed. The following data must be recorded:

- **Clinical parameters:** age, sex, height, weight, body mass index, body surface, cardiovascular risk factors, medication intake, background interests, history of heart disease, presence of ischemic heart disease, cerebrovascular accident, peripheral artery disease, chronic obstructive pulmonary disease, symptoms (angina, syncope, dyspnea according to grades of the NYHA, other symptoms), blood pressure, heart rate, evidence of heart failure, assessment of functional class by means of 6MT and fragility assessment.
- **Analytical parameters:** hematocrit, NT-proBNP, Troponin I, electrolytes, C-reactive protein, creatinine, glomerular filtrate.
- **Protein electrophoresis:** Rating presence of the monoclonal component
- **Scintigraphy with TC⁹⁹:** Assessment of values of tracer uptake.
- **Device parameters:** Type of prosthesis, dimensions, expandable/ self-expanding ball, post-dilatation.
- **ECG parameters:** Rhythm, PR duration, pacemakers, implantable cardioverter defibrillator, QRS duration.

- The 6 minute-test: All patients in the study will have a test of 6 minutes before implantation and 6 months follow-up, according to the protocol after a TAVI, in order to carry out an objective functional assessment of the functional capacity. The distance covered will be determined, the variation of oxygen saturation by means of non-invasive pulse oximetry before and after the test and the appearance of symptoms with the effort according to the Borg scale.

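### The single Basal visit has conflicting timing relative to implantation, so baseline ECG, pacing status and strain may be recorded after TAVI

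*Combined protocol and SAP*

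**What the plan says.** The schedule has one baseline time point, called Basal in Sections 11.2 and 12. Its timing has to be pieced together.

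- Section 11.1 on the walk test: "All patients in the study will have a test of 6 minutes before implantation and 6 months follow-up".
- Section 11.2 lists under the Basal visit an electrocardiogram, laboratory analysis, "Echocardiographic basal study, with ventricular" strain measurements, and "Perform 6-minute test".
- Section 11.1 lists the ECG items: "Rhythm, PR duration, pacemakers, implantable cardioverter defibrillator, QRS duration". It gives them no time relative to implantation. The same initial assessment records device details: "Type of prosthesis, dimensions, expandable/ self-expanding ball, post-dilatation".
- Section 13.1 has eligibility checked and consent taken first. It then says that basal clinical, laboratory, ECG, echo, functional and scintigraphy data "of the patient will be collected before discharge".
- Section 9.2 makes the valve replacement itself an inclusion criterion. Section 9.3 excludes patients who die in hospital from a procedural complication.
- Section 11.2 opens the follow-up series thus: "This will be done before discharge, in consultation at three, six, and 12 months and annually thereafter". The Section 1 summary also counts the pre-discharge contact as follow-up. Neither the visit list in 11.2 nor the table in Section 12 has an entry for it, and events assessment first appears at 3 months.

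**The concern.** Secondary objective 1 concerns permanent pacemaker implantation, pacemaker dependence and changes in the conduction system. Section 4 lists among the problems of TAVI "Atrioventricular conduction disorders requiring permanent pacemaker implantation in 20-40% of the patients". If PR, QRS and pacing status are first recorded after the valve is in, the starting point already contains whatever the procedure did to conduction, and change measured from it misses the early part.

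Objective 3 follows the evolution of strain patterns and needs a starting point that is the same for every patient. Objective 2 uses the walk test, for which 11.1 and 13.1 give different time references.

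In a multicentre study, one site may follow 11.1 and another 13.1, and they would enter different quantities in the same field. A pre-implant ECG or strain study that was not done cannot be obtained once the valve is in place.

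**Working it through.** The plan states no figure on this point, so the check is a comparison of the text, followed by one multiplication for scale.

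**Step 1. Text pointing to a Basal visit before implantation.**
- 11.1 dates the baseline walk test before implantation, and 11.2 puts that test in the Basal visit with the ECG and strain echo.
- Section 9 describes the amyloidosis cohort as patients whose TAVI is still to come.
- 9.1 recruits from wards and clinics on echocardiographic criteria for severe stenosis.
- 11.1 describes an inclusion visit that assesses a candidate.

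**Step 2. Text pointing to a Basal visit after implantation.**
- 13.1 orders the steps as eligibility, then consent, then basal data, with discharge as the time limit. Eligibility under 9.2 and 9.3 cannot be settled until the valve is in and in-hospital survival is known.
- 11.1 includes post-dilatation, which is known only after the procedure.
- Sections 1 and 11.2 treat the pre-discharge contact as the first follow-up contact, yet the first entry in the 11.2 visit list is the Basal visit.

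**Step 3. Is any item other than the walk test anchored?** No section requires the baseline ECG, pacing status, strain echo or laboratory tests to precede implantation.

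**Step 4. Does the rest of the schedule make up for it?** After Basal, the next scheduled ECG is at 6 months in the Section 12 table and at 12 months in the 11.2 list. With one early time point, a site that takes the ECG before TAVI has no scheduled early ECG after it, and a site that takes it after TAVI has none before it. Section 10.1 names Kaplan-Meier and Cox methods but gives no time origin, so the analysis plan does not settle the matter.

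**Step 5. Scale.** Inputs: pacemaker rate 20-40% (Section 4); planned size 321 (Section 10, sample size).
- Lower: 321 × 0.20 = 64.2, about 64 patients.
- Upper: 321 × 0.40 = 128.4, about 128 patients.

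Let *s* be the share of these devices implanted before a post-TAVI Basal assessment. The number already present at that assessment is *s* × 64 to *s* × 128. The documents do not give *s*. If every patient were assessed after TAVI, the count could lie anywhere from 0 (*s* = 0) to 128 (*s* = 1 at the upper rate).

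**The case against.** The strongest reply is that 13.1 only sets a deadline. A patient admitted for TAVI has not been discharged either before or after the procedure, and 13.1 refers back to the predefined protocol. The only baseline test with an explicit anchor is placed before implantation, in the same visit as the ECG and strain echo. The in-hospital-death exclusion fits patients enrolled beforehand and removed later. The device items show when the record is completed, not when the ECG is taken. All of this stands, so a reader who infers that the protocol orders a post-implant baseline goes too far. What remains is an unresolved conflict that permits one.

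Four other inferences are tempting, and the documents do not support them.

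- **In-hospital pacemakers drop out of the event count.** No rule says that a device present at the Basal visit is not an event. Section 1 lists pacemaker implantation among the events and places the pre-discharge contact within follow-up. An events assessment at 3 months could look back to implantation, although the plan does not say that it does. A site could read such a device as baseline status; the plan does not tell it to.
- **Different timing between sites confounds the amyloidosis comparison.** Both cohorts share one schedule. Confounding would require timing to be related to amyloid status, and nothing suggests that it is.
- **Strain is altered by the valve replacement.** This is a reasonable inference, but the documents do not state it. The point on objective 3 needs only that the starting point is undefined.
- **The primary comparison is compromised.** Two-year mortality and heart-failure admissions do not depend on when the baseline ECG or strain was taken.

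**Conclusion.** The concern holds as a conflict over when the one Basal visit takes place, together with a missing pre-discharge entry. A site can comply with 13.1 and still have no ECG or strain study from before implantation. The parts at risk are conduction change in secondary objective 1, the starting point for strain evolution in objective 3, and any Cox model that uses baseline ECG or echo covariates. The risk is conditional on a site measuring after TAVI; how many would do so cannot be judged from the documents.

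The only supportable figure is that about 64 to 128 of 321 patients would receive a pacemaker, taking the general TAVI rate in Section 4 as applying to this study. The number misread as baseline status cannot be estimated. With the primary comparison little affected, this is a clarification that should be made because it is cheap and the loss cannot be repaired later.

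**What to change.** 1. In 11.1, 11.2, 12 and 13.1, define the baseline ECG, pacing status, strain echo, laboratory tests and 6-minute test as the last values before implantation. Allow routine pre-TAVI records to supply them once the patient has consented.
2. Add a pre-discharge visit to 11.2 and a matching column in Section 12, holding device data, a post-TAVI ECG and in-hospital events, including new pacemakers.
3. In 10.1, state that new pacemakers and conduction change are counted from the day of implantation.
4. Leave patients without a pre-implant ECG or strain study out of the corresponding change analyses only, and keep them in the cohort. Report their number in each cohort.

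The cost is protocol wording and one additional case-report-form column; the pre-discharge contact is already promised in Sections 1 and 11.2. The downside is some missing baseline data. Section 9.1 implies an echo before TAVI but does not mention an ECG, and a routine echo may not meet the strain acquisition requirements in Annex I.
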